### **3.2.2 Ofatumumab Adverse Events**

During clinical trials of ofatumumab in FL, CLL and RA subjects, adverse events occurring during the infusions of trial drug have been reported. The following reactions should be regarded as expected infusion-related adverse reactions in connection with the use of ofatumumab probably as a consequence of B cell depletion and cytokine release: pruritus, dyspnea, bronchospasm, throat irritation, cough, pharyngolaryngeal pain, flushing, hyperhidrosis, nausea and vomiting, abdominal pain, hypotension, rash/urticaria, influenza-like-illness, fatigue, fever, chills, headache, dizziness, myalgia and arthralgia.

The incidence of infusion-related symptoms was highest during the first infusion and decreased substantially with subsequent infusions. Implementation of pre-medication before infusions has reduced the number as well as the severity of infusion related adverse events. One serious case of cytokine release complicated with laryngeal edema and one case of anaphylactoid-like reaction have been observed; both events were fully reversible after cessation of the infusion and proper treatment. It should be noted that none of these subjects received premedication with prednisolone.

During the ongoing study in subjects with CLL refractory to alemtuzumab and fludarabine, infusion related adverse events have been reported in approximately 30% of subjects. Only 2-3 % were serious adverse events. All subjects received pre-medication with prednisolone, acetaminophen and antihistamine. In the completed CLL trial 402 in patients with relapsed or refractory CLL, 15% of the subjects had serious infections. In the ongoing CLL 406 trial in subjects refractory to both alemtuzumab and fludarabine an increased frequency of serious infections (25-30%) have been reported.

---

Subjects who are HBsAg negative, anti-HBc positive and HBV DNA negative may be included in the study but must undergo HBV DNA monitoring. Consult with a physician experienced in care & management of subjects with hepatitis B to manage/treat subjects who are anti-HBc positive. Initiate anti-viral therapy if required. If a subject's HBV DNA becomes positive during the study, notify the NOVARTIS medical monitor. For subjects who have not completed planned ofatumumab therapy, discuss with the medical monitor the risks and benefits of continuing or discontinuing ofatumumab before appropriate treatment decisions are made for that individual subject.

One case of Progressive Multifocal Leukoencephalopathy (PML) has been reported in a very ill CLL subject previously treated with alemtuzumab and fludarabine and with a very low CD4 cell count. Leukopenia, including neutropenia, anemia, and thrombocytopenia have been reported in CLL subjects. These events are most likely related to the patients' baseline disease; however, a causal relationship to ofatumumab cannot be excluded.

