 Cycle 4 may begin up to 14 days after cycle 3 bone marrow biopsy to allow for results of response assessments to be available.

 CBC and CMP only every 4 weeks. See Section 5.8. Any grade 3 or 4 cytopenia will be recorded as an adverse event during Maintenance Therapy. No other adverse events will be recorded during Maintenance Therapy

 Upon discontinuation of study therapy, any diagnostic testing will be at the discretion of the physician.

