A Phase II trial of single agent lenalidomide in patients with relapsed or refractory CLL revealed an ORR of 47% with a CR rate of 9%.  Another phase II trial of single agent lenalidomide for the treatment of relapsed or refractory CLL revealed an ORR of 32% with 7% CR, 25% stable disease. The most common toxicity was myelosuppression, and the median daily dose of lenalidomide tolerated was 10 mg.  More recently two combination trials of lenalidomide and rituximab have been reported in abstract form from our center  and MDACC.  Both these studies evaluated patients in the relapsed setting and had an overall response rate of 60%.

Our hypothesis is that ofatumumab will produce higher rates of CR when combined with lenalidomide and high dose steroids. The consolidation with lenalidomide is based on the fact that this drug has activity in CLL but is not immunosuppressive. In addition, there is evidence that lenalidomide can improve the immune system of patients with CLL as well as increase the rates of CR in this population. The reason for incorporating lenalidomide after debulking patients with high dose steroids and ofatumumab is based on the experience with lenalidomide as a single agent in the relapsed and front line setting. In this setting tumor lysis syndrome and tumor flare were observed. We believe that this sequence of drugs will carry less toxicity and will be better tolerated.

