### **6.1.1 Adverse Event Reporting**

Toxicity will be scored using CTCAE Version 4.0 for toxicity and adverse event reporting. A copy of the CTCAE Version 4.0 can be downloaded from the CTEP homepage (<HTTP://CTEP.INFO.NIH.GOV>). All appropriate treatment areas should have access to a copy of the CTCAE Version 4.0. All adverse clinical experiences, whether observed by the investigator or reported by the patient, must be recorded, with details about the duration and intensity of each episode, the action taken with respect to Amendment 5 Dated 03/02/2016

---

the test drug, and the patient's outcome. The investigator must evaluate each adverse experience for its relationship to the test drug and for its seriousness.

The investigator must appraise all abnormal laboratory results for their clinical significance. If any abnormal laboratory result is considered clinically significant, the investigator must provide details about the action taken with respect to the test drug and about the patient's outcome.

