### **Adverse Events:**

Any untoward medical occurrence in a subject or clinical investigation subject, temporally associated with the use of a medicinal product, whether or not considered related to the medicinal product.

Events meeting the definition of an AE include:

- Any abnormal laboratory test results (hematology, clinical chemistry, or urinalysis) or other safety assessments e.g., ECGs, radiological scans, vital signs measurements), including those that worsen from baseline, and felt to be clinically significant in the medical and scientific judgment of the investigator
- Exacerbation of a chronic or intermittent pre-existing condition including either an increase in frequency and/or intensity of the condition
- New conditions detected or diagnosed after investigational product administration even though it may have been present prior to the start of the study
- Signs, symptoms, or the clinical sequelae of a suspected interaction
- Signs, symptoms, or the clinical sequelae of a suspected overdose of either investigational product or a concomitant medication (overdose per se will not be reported as an AE/SAE)

“Lack of efficacy” or “failure of expected pharmacological action” per se will not be reported as an AE or SAE. However, the signs and symptoms and/or clinical sequelae resulting from lack of efficacy will be reported if they fulfill the definition of an AE or SAE.

Events that **do not** meet the definition of an AE include:

Amendment 5 Dated 03/02/2016

---

- Any clinically significant abnormal laboratory finding or other abnormal safety assessments that is associated with the underlying disease, unless judged by the investigator to be more severe than expected for the subject's condition.
- The disease/disorder being studied, or expected progression, signs, or symptoms of the disease/disorder being studied, unless more severe than expected for the subject's condition
- Medical or surgical procedure (e.g., endoscopy, appendectomy); the condition that leads to the procedure is an AE
- Situations where an untoward medical occurrence did not occur (social and/or convenience admission to a hospital)
- Anticipated day-to-day fluctuations of pre-existing disease(s) or condition(s) present or detected at the start of the study that do not worsen
- B cell depletion and hypogammaglobulinemia due to ofatumumab treatment

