#### **6.2.2 Laboratory and Other Safety Assessment Abnormalities Reported as AEs and SAEs**

- Any abnormal laboratory test results (hematology, clinical chemistry, or urinalysis) or other safety assessments (e.g., ECGs, radiological scans, vital signs

measurements), including those that worsen from baseline, and felt to be clinically significant in the medical and scientific judgment of the investigator **are** to be recorded as AEs or SAEs.

- All events meeting liver stopping criteria must be recorded as an SAE.
- However, any clinically significant safety assessments that are associated with the underlying disease, unless judged by the investigator to be more severe than expected for the subject's condition, are **not** to be reported as AEs or SAEs.
- B cell depletion, IgG below LLN, low CD19+ count, and hypogammaglobulinemia due to treatment with ofatumumab are **not** to be reported as AEs or SAEs.
- Infusion related AEs may lead to a prolonged infusion time. Overnight stay at the hospital due to slow infusion rate is **not** to be reported as a SAE.

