#### **10.5 Toxicity Monitoring and Stopping Rules**

All patients will be evaluable for toxicity and adverse events from the time of their first protocol treatment. Toxicity will be reported by type and severity according to the CTCAE version 4.0.

During the entire study period, toxicity will be closely monitored by the PI and clinical trial coordinator of this study, even though no formal stopping rules are stipulated in this protocol. In the event that toxicity is thought to be excessive for the study patient population at any point of the trial, the patient accrual to the trial will be suspended immediately, pending a review of all toxicity data. A final decision will be made by the PI and sponsor as to whether the trial should be amended, terminated or continue accrual. Such decision should be filed with and pre-approved by the institutional Protocol Monitoring Committee.

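### Grade 3 or 4 cytopenias in cycles 1-12 that are attributed to CLL can be left out of the toxicity results, because Section 10.5 does not say which adverse-event definition applies

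*Combined protocol and SAP*

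**What the plan says.** Section 6 has adverse events recorded from the first dose, entered in the database on day 1 of each cycle and graded by CTCAE v4.0. It does not define an adverse event. Section 6.1.1 states "All adverse clinical experiences, whether observed by the investigator or reported by the patient, must be recorded", and asks for action taken and outcome for any clinically significant abnormal laboratory result. It makes no exception for disease.

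The only explicit definition is in Section 6.2, on reporting to Novartis. Its list of what counts includes clinically significant hematology results, among them those that worsen from baseline. Its list of what does not count begins "Any clinically significant abnormal laboratory finding or other abnormal safety assessments that is associated with the underlying disease", with an exception where the investigator judges the finding worse than the patient's condition would lead one to expect. Section 6.2.2 repeats this for adverse events and serious adverse events: "any clinically significant safety assessments that are associated with the underlying disease" are not to be reported, with the same exception.

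Maintenance has its own rule (Section 2, footnote 14): "Any grade 3 or 4 cytopenia will be recorded as an adverse event during Maintenance Therapy". Sections 5.8 and 6 say the same. None of the three applies an attribution test.

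Section 10.5 says "Toxicity will be reported by type and severity according to the CTCAE version 4.0" and does not name the definition that supplies the events.

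Two background statements give context. Section 3.2.2, on earlier ofatumumab experience with cytopenias, reads "These events are most likely related to the" patients' "baseline disease; however, a causal relationship to ofatumumab cannot be excluded". Section 3.5 says of a lenalidomide trial: "The most common toxicity was myelosuppression".

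**The concern.** In CLL, a falling neutrophil, platelet or hemoglobin value may come from the disease, the treatment or both. Inclusion criterion 8 sharpens the question, because it waives the neutrophil and platelet minimums when the marrow is extensively involved. The two lists in Section 6.2 give opposite answers for such a fall, and no tie-break is stated. If the exclusion is followed, the investigator's attribution decides whether the event is counted.

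A single-arm trial has no control group to show how many cytopenias the disease alone would have produced. Lower toxicity than conventional regimens is part of the stated rationale, and myelosuppression is the main toxicity named for lenalidomide. The cytopenia rate is therefore a figure that readers will look for. Section 10.5 has no formal toxicity boundary and relies on a judgment that toxicity is excessive, so an incomplete event listing would also give that judgment less to work with.

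**Working it through.** The plan states no cytopenia rate, so it has no figure of its own to reproduce. The check has three parts.

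**1. One event taken through the rules.** Suppose a patient has grade 4 neutropenia in cycle 2, and the investigator attributes it to CLL and regards it as expected.

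- Section 6.2, inclusion list: an adverse event, if the value has worsened from baseline and is judged clinically significant.
- Sections 6.2 and 6.2.2, exclusion: not an adverse event.
- Section 6.1.1: action and outcome are documented if the value is clinically significant, whatever the cause.
- Section 10.5: silent on whether the event enters the toxicity table.
- The same event in maintenance: recorded.

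**2. Would the event show up as progression instead?** Appendix F gives these progression criteria for blood counts attributed to CLL:

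- Neutrophils: none. A disease-attributed neutropenia could appear in neither the toxicity nor the response results.
- Platelets: a fall of at least 50%. Take a patient admitted at 45,000 under the criterion 8 waiver who falls to 24,000. The fall is (45,000 − 24,000)/45,000 = 46.7%, which is not progression. Yet the count is below 25,000, which Table 2 of Section 5.5.3.6 labels grade 4.
- Hemoglobin: a fall of at least 2 g/dL. Falls that meet the platelet or hemoglobin criterion would be visible as progression, though not as toxicity.

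**3. Direction and size.** Let T be the number of patients with a grade 3 or 4 cytopenia and f the share set aside as disease-related. The table then shows T × (1 − f), which cannot exceed T and equals T when f = 0.

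The documents give neither T nor f, so the values below are assumptions. The sample size is the planned maximum of 45 (Section 10.2). Counts are 45 × rate × (1 − f), rounded to whole patients with halves going to the even number. Intervals are exact (Clopper-Pearson) 95%: the lower limit is the 0.025 quantile of Beta(x, 45 − x + 1) and the upper limit is the 0.975 quantile of Beta(x + 1, 45 − x).

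| Assumed true count | None set aside | A quarter set aside | Half set aside |
|---|---|---|---|
| 9/45 | 20% (9.6-34.6) | 7/45, 16% (6.5-29.5) | 4/45, 9% (2.5-21.2) |
| 18/45 | 40% (25.7-55.7) | 14/45, 31% (18.2-46.6) | 9/45, 20% (9.6-34.6) |
| 27/45 | 60% (44.3-74.3) | 20/45, 44% (29.6-60.0) | 14/45, 31% (18.2-46.6) |

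In the middle row with half set aside, the upper limit of 34.6% lies below the assumed 40%. That 40% is itself an assumed sample proportion with a wide interval, so the table shows what could happen and does not estimate what will.

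**The case against.** The strongest reply is about scope. The exclusion sits in a section on reporting to Novartis, trial-wide collection is set in Section 6, and Section 10.5 applies no attribution filter. On that reading the toxicity tables are already complete. Much of this stands, but two things leave the boundary unclear. Section 6.2 is the only place where an adverse event is defined, and the inclusion bullet of Section 6.2.2 speaks of recording laboratory findings, not only of reporting them. Section 10.5 does not choose between the definitions.

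It can also be said that the maintenance rule narrows collection to cytopenias and so implies that they were already collected in cycles 1-12. That is a reasonable reading, but the protocol does not state it, and the disease-associated exclusion points the other way.

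The exclusion has limits too. It does not cover findings judged worse than expected. Only patients with CR, PR or SD enter cycles 4-12, and attributing a large platelet or hemoglobin fall to CLL would mean declaring progression. These limits reduce the likely number of omitted events, but they do not cover neutropenia or platelet falls short of 50%.

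Four stronger readings are tempting, and the documents do not support them.

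- Section 3.2.2 might be taken to settle attribution in favor of disease. It is background on ofatumumab alone, leaves causality open and sets no recording rule. Section 3.4 lists cytopenias among lenalidomide adverse events regardless of presumed relationship.
- Section 6.1.1 might be taken to make every grade 3 or 4 value an adverse event. Its laboratory rule turns on clinical significance.
- A lenalidomide hold under Table 2 might seem to contradict non-recording. Dose rules and event classification serve different purposes, and Section 6.1.1 would still require the action to be documented for a clinically significant result.
- Disease attribution might seem available for any cytopenia. The limits above show that it is not.

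**Conclusion.** The point holds as an unresolved recording rule. Applied as written, Sections 6.2 and 6.2.2 allow a grade 3 or 4 cytopenia in cycles 1-12 to be left out of the toxicity results when the investigator attributes it to CLL and does not judge it worse than expected. Section 10.5 does not prevent this. The clearest contrast is with maintenance, where the same event must be recorded. The difference from Section 6.1.1 is one of scope more than direct contradiction.

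Any error in the reported rate from this source is downward. Its size is unknown: it depends on the true rate and on the share attributed to disease, and it is zero if no event is so attributed. A reader might infer that the published rates will be materially too low, but the documents give no rates from which to conclude that.

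Severity is minor. Toxicity is neither an objective nor an endpoint in Section 4, the response-rate decision is unaffected, and no stopping boundary depends on these counts.

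**What to change.** In Sections 6 and 10.5, state that every grade 3 or 4 neutropenia, anemia and thrombocytopenia from first dose through cycle 12 is recorded in the study database and tabulated regardless of attribution, with attribution kept as a separate field.

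Add to Section 10.5 a table of worst laboratory-derived CTCAE grade, with shift from baseline grade, separately for cycles 1-3 and cycles 4-12. The blood counts scheduled in Section 2 supply the data.

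Report maintenance cytopenias separately, from the adverse-event entries already required there. Section 5.8 says that maintenance blood counts are not recorded in the database, so a laboratory-derived shift table for that phase would need new data capture. Monitoring frequency also differs, so maintenance and earlier rates should not be read as directly comparable.

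In Sections 6.2 and 6.2.2, state that the disease-associated exclusion governs reporting to Novartis only.

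The cost is a few sentences and one table, with no new visits or tests. It assumes that blood counts in cycles 1-12 are entered in the database, which the maintenance exemption implies but the protocol does not say outright. The downside is more adverse-event entries and somewhat higher stated cytopenia rates, some of them due to disease. The shift table lets the reader see the part already present at baseline.

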### **3.3 High Dose Methylprednisolone**

Methylprednisolone is a corticosteroid that has been on the market for several years and is available in generic form.

Results of a phase II study combining Rituximab, an anti CD20 monoclonal antibody, with high dose methylprednisolone as salvage regimen for the treatment of patient with fludarabine refractory CLL showed an overall response rate (ORR) of 93% with a complete remission rate (CR) of 36%. The regimen was well tolerated and serious adverse events were rare. All patients were able to complete the scheduled treatment without delays or dosage reductions.  Another recent paper from the same group showed a similar efficacy in the front line setting using a reduced dose of steroids. They showed an ORR of 96% with a CR rate of 32%. 

### 3.3.1 Methylprednisolone Adverse Effects

The following adverse events have been reported with the use of methylprednisolone and are common to most corticosteroids: arrhythmias, bradycardia, cardiac arrest, cardiomegaly, circulatory collapse, congestive heart failure, edema, fat embolism, hypertension in premature infants, myocardial rupture (post MI), syncope, tachycardia, thromboembolism, vasculitis, delirium, depression, emotional instability, euphoria, hallucinations, headache, intracranial pressure increased, insomnia, malaise, mood swings, nervousness, neuritis, personality changes, psychic disorders, pseudotumor cerebri (usually following discontinuation), seizure, vertigo, acne, allergic dermatitis, alopecia, dry scaly skin, ecchymoses, edema, erythema, hirsutism, hyper-/hypopigmentation, hypertrichosis, impaired wound healing, petechiae, rash, skin atrophy, sterile abscess, skin test reaction impaired, striae, urticaria, adrenal suppression, amenorrhea, carbohydrate intolerance increased, Cushing's syndrome, diabetes mellitus, fluid retention, glucose intolerance, hyperglycemia, hyperlipidemia, hypokalemia, hypokalemic alkalosis, menstrual irregularities, negative nitrogen balance, pituitary-adrenal axis suppression, protein catabolism, sodium and water retention, abdominal distention, appetite increased, gastrointestinal hemorrhage, gastrointestinal perforation, nausea, pancreatitis, peptic ulcer, perforation of the small and large intestine, ulcerative esophagitis, vomiting, weight gain, leukocytosis (transient), hepatomegaly, increased transaminases, arthralgia, arthropathy, aseptic necrosis (femoral and humoral heads), fractures, muscle mass loss, muscle weakness, myopathy (particularly in conjunction with neuromuscular disease or neuromuscular-blocking agents), neuropathy, osteoporosis, parasthesia, tendon rupture, vertebral compression fractures, weakness, cataracts, exophthalmoses, glaucoma, intraocular pressure increased, glycosuria, pulmonary edema, abnormal fat disposition, anaphylactoid reaction, anaphylaxis, angioedema, avascular necrosis, diaphoresis, hiccups, hypersensitivity reactions, infections, secondary malignancy

### 3.4 Lenalidomide

Lenalidomide (Revlimid®) is a proprietary IMiD® compound of Celgene Corporation.

IMiD® compounds have both immunomodulatory and anti-angiogenic properties which

Amendment 5 Dated 03/02/2016

could confer antitumor and antimetastatic effects. Lenalidomide has been demonstrated to possess anti-angiogenic activity through inhibition of bFGF, VEGF and TNF- $\alpha$  induced endothelial cell migration, due at least in part to inhibition of Akt phosphorylation response to bFGF. In addition, lenalidomide has a variety of immunomodulatory effects. Lenalidomide stimulates T cell proliferation, stimulates the production of IL-2, IL-10 and IFN-gamma, inhibits IL-1 beta and IL-6, and modulates IL-12 production. Up regulation of T cell derived IL-2 production is achieved at least in part through increased AP-1 activity.

Although the exact antitumor mechanism of action of lenalidomide is unknown, a number of mechanisms are postulated to be responsible for lenalidomide's activity against multiple myeloma. Lenalidomide has been shown to increase T cell proliferation, which leads to an increase in IL-2 and IFN- $\gamma$  secretion. The increased level of these circulating cytokines augment natural killer cell number and function, and enhance natural killer cell activity to yield an increase in multiple myeloma cell lysis. In addition, lenalidomide has direct activity against multiple myeloma and induces apoptosis or G1 growth arrest in multiple myeloma cell lines and in multiple myeloma cells of patients resistant to melphalan, doxorubicin and dexamethasone.

